### **9.3 Clinical Study Report and Publications**

A Signatory Investigator must be selected to sign the clinical study report.

For this protocol, the Signatory Investigator will be selected as appropriate based on the following criteria:

- External Principal Investigator designated at protocol development
- Other criteria (as determined by the study team)

The data collected during this study are confidential and proprietary to BMS or designee. Any publications or abstracts arising from this study must adhere to the publication requirements set forth in the clinical trial agreement (CTA) governing [Study site or Investigator] participation in the study. These requirements include, but are not limited to, submitting proposed publications to BMS or designee at the earliest practicable time prior to submission or presentation and otherwise within the time period set forth in the CTA.

## 10 GLOSSARY OF TERMS

Term	Definition
Complete Abstinence	Complete Abstinence is defined as complete avoidance of heterosexual intercourse and is an acceptable form of contraception for all study drugs. This also means that abstinence is the preferred and usual lifestyle of the patient. This does not mean periodic abstinence (eg, calendar, ovulation, symptothermal, profession of abstinence for entry into a clinical trial, post-ovulation methods) and withdrawal, which are not acceptable methods of contraception. Women must continue to have pregnancy tests. Acceptable alternate methods of highly or less effective contraception's must be discussed in the event that the subject chooses to forego complete abstinence.
PD-L1 Evaluable Status	Sufficient quantity of tissue sample available for analysis
PD-L1 Indeterminate Status	Inconclusive result

## 11 LIST OF ABBREVIATIONS

Term	Definition
AE	adverse event
ADA	Anti Drug Antibody
AIDS	Acquired Immunodeficiency Syndrome
AST	aspartate aminotransferase
AT	aminotransaminases
AUC	area under the concentration-time curve
BICR	Blinded Independent Central Review
BLQ	below limit of quantification
BMI	body mass index
BMS	Bristol-Myers Squibb
BP	blood pressure
BSA	Body surface area
BSC	Best Supportive Care
BUN	blood urea nitrogen
C	Celsius
Ca ++	calcium
C avg	average concentration
CBC	complete blood count
CFR	Code of Federal Regulations
CI	confidence interval
Cl 	chloride
CrCl	creatinine clearance
CLR	renal clearance
CLT	total body clearance
cm	centimeter
C max , C MAX	maximum observed concentration
C min , C MIN	trough observed concentration
CNS	Central nervous system
CRF	Case Report Form, paper or electronic

Term	Definition
CV	coefficient of variation
CR	Complete response
CT	computerized tomography
DCR	Disease Control rate
dL	deciliter
DILI	Drug Induced Liver Injury
EAC	Esophageal Adenocarcinoma
EBV	Epstein-Barr Virus
EC	Esophageal Cancer
ECOG	Eastern Cooperative Oncology Group
eCRF	Electronic Case Report Form
ECS	Esophageal Cancer Subscale
EDC	Electronic Data Capture
eg	exempli gratia (for example)
EoT	End of treatment
ESCC	Esophageal Squamous Cell Cancer
ESMO	European Society of Medical Oncology
FA	final analysis
FACT-G7	Functional Assessment of Cancer Therapy - General
FACT-Ga	Functional Assessment of Cancer Therapy - Gastric
FACT-E	Functional Assessment of Cancer Therapy - Esophageal
FDA	Food and Drug Administration
FFPE	Formalin-Fixed Paraffin-Embedded
FSH	follicle stimulating hormone
g	gram
GaCS	Gastric Cancer Subscale
GC	Gastric Cancer
GCP	Good Clinical Practice
GEC	Gastric-Esophageal Junction Cancer
GERD	Gastro-Esophageal Reflux Disease
GFR	glomerular filtration rate

Term	Definition
h	hour
HBsAg	hepatitis B surface antigen
HBV	hepatitis B virus
hCG	Human chorionic gonadotropin
HCV	hepatitis C virus
HIPAA	Health Insurance Portability and Accountability Act
HIV	Human Immunodeficiency Virus
HR	heart rate hazard ratio
HRT	hormone replacement therapy
IA	interim analysis
IB	Investigator Brochure
ICH	International Conference on Harmonisation
ie	id est (that is)
IEC	Independent Ethics Committee
IFN	Interferon
IMG	Immunogenicity
IMP	investigational medicinal products
IND	Investigational New Drug
IO	Immuno-Oncology
IRB	Institutional Review Board
IRCC	Immune related Response Criteria
IRT	Interactive Response Technology
IU	International Unit
IV	intravenous
K+	potassium
kg	kilogram
L	liter
LDH	lactate dehydrogenase
mg	milligram

Term	Definition
Mg ++	magnesium
min	minute
mL	milliliter
MLR	Mixed Lymphocytes reaction
mmHg	millimeters of mercury
mOS	Median overall survival
mDOR	Median duration of response
MRI	Magnetic resonance imaging
MSI	Microsatellite Instability
MTD	maximum tolerated dose
µg	microgram
N	number of subjects or observations
Na +	sodium
N/A	not applicable
NCCN	National Comprehensive Cancer Network
ng	nanogram
NIMP	non-investigational medicinal products
NSCLC	Non Small Cell Lung Cancer
OS	Overall Survival
ORR	Objective Response Rate
PBMC	Peripheral Blood Mononuclear cell
PD	Disease Progression
PD-L1	Programmed Death Ligand 1
PFS	Progression Free Survival
PK	pharmacokinetics
PPK	Population pharmacokinetic
PRO	Patient Reported Outcomes
QxW	Every x weeks
QoL	Quality of Life
RCC	Renal Cell Carcinoma

Term	Definition
RECIST	Response Evaluation Criteria In Solid Tumors
RT PCR	Real-time Polymerase Chain Reaction
SAE	serious adverse event
SAP	statistical analysis plan
SD	standard deviation
SNP	Single Nucleotide Polymorphism
SOC	Standard of Care
SOP	Standard Operating Procedures
SPC	Summary of Product Characteristic
Subj	subject
t	temperature
T	time
T-HALF	Half life
TCR	T-cell receptor
TMB	Tumor mutational burden
TSST	Time to second subsequent therapy
TTP	Time to progression
TTR	Time to response
V c	Volume of Central compartment
V ss /F (or V ss )	apparent volume of distribution at steady state
V z	Volume of distribution of terminal phase (if IV and if multi-exponential decline)
WBC	white blood cell
WHO	World Health Organization
WOCBP	women of childbearing potential

## **APPENDIX 1      MANAGEMENT ALGORITHMS**

These general guidelines constitute guidance to the Investigator and may be supplemented by discussions with the Medical Monitor representing the Sponsor. The guidance applies to all immuno-oncology agents and regimens.

A general principle is that differential diagnoses should be diligently evaluated according to standard medical practice. Non-inflammatory etiologies should be considered and appropriately treated.

[figure not shown]
Corticosteroids are a primary therapy for immuno-oncology drug-related adverse events. The oral equivalent of the recommended IV doses may be considered for ambulatory patients with low-grade toxicity. The lower bioavailability of oral corticosteroids should be taken into account when switching to the equivalent dose of oral corticosteroids.

Consultation with a medical or surgical specialist, especially prior to an invasive diagnostic or therapeutic procedure, is recommended.

The frequency and severity of the related adverse events covered by these algorithms will depend on the immuno-oncology agent or regimen being used.

## GI Adverse Event Management Algorithm

Rule out non-inflammatory causes. If non-inflammatory cause is identified, treat accordingly and continue I-O therapy. Opiates/narcotics may mask symptoms of perforation. Infliximab should not be used in cases of perforation or sepsis.

[figure not shown]

Patients on IV steroids may be switched to an equivalent dose of oral corticosteroids (e.g. prednisone) at start of tapering or earlier, once sustained clinical improvement is observed. Lower bioavailability of oral corticosteroids should be taken into account when switching to the equivalent dose of oral corticosteroids.

27-Jun-2018

## Renal Adverse Event Management Algorithm

Rule out non-inflammatory causes. If non-inflammatory cause, treat accordingly and continue I-O therapy.

[figure not shown]

Patients on IV steroids may be switched to an equivalent dose of oral corticosteroids (e.g. prednisone) at start of tapering or earlier, once sustained clinical improvement is observed. Lower bioavailability of oral corticosteroids should be taken into account when switching to the equivalent dose of oral corticosteroids.

27-Jun-2018

## Pulmonary Adverse Event Management Algorithm

Rule out non-inflammatory causes. If non-inflammatory cause, treat accordingly and continue I-O therapy. Evaluate with imaging and pulmonary consultation.

[figure not shown]
Patients on IV steroids may be switched to an equivalent dose of oral corticosteroids (e.g. prednisone) at start of tapering or earlier, once sustained clinical improvement is observed. Lower bioavailability of oral corticosteroids should be taken into account when switching to the equivalent dose of oral corticosteroids

27-Jun-2018

## Hepatic Adverse Event Management Algorithm

Rule out non-inflammatory causes. If non-inflammatory cause, treat accordingly and continue I-O therapy. Consider imaging for obstruction.

[figure not shown]
Patients on IV steroids may be switched to an equivalent dose of oral corticosteroids (e.g. prednisone) at start of tapering or earlier, once sustained clinical improvement is observed. Lower bioavailability of oral corticosteroids should be taken into account when switching to the equivalent dose of oral corticosteroids.

\*The recommended starting dose for grade 4 hepatitis is 2 mg/kg/day methylprednisolone IV.

27-Jun-2018

## Endocrinopathy Adverse Event Management Algorithm

Rule out non-inflammatory causes. If non-inflammatory cause, treat accordingly and continue I-O therapy. Consider visual field testing, endocrinology consultation, and imaging.

[figure not shown]

Patients on IV steroids may be switched to an equivalent dose of oral corticosteroids (e.g. prednisone) at start of tapering or earlier, once sustained clinical improvement is observed. Lower bioavailability of oral corticosteroids should be taken into account when switching to the equivalent dose of oral corticosteroids.

27-Jun-2018

## Skin Adverse Event Management Algorithm

Rule out non-inflammatory causes. If non-inflammatory cause, treat accordingly and continue I-O therapy.

Patients on IV steroids may be switched to an equivalent dose of oral corticosteroids (e.g. prednisone) at start of tapering or earlier, once sustained clinical improvement is observed. Lower bioavailability of oral corticosteroids should be taken into account when switching to the equivalent dose of oral corticosteroids.

[figure not shown]
\*Refer to NCI CTCAE v4 for term-specific grading criteria.

\*\*If SJS/TEN is suspected, withhold I-O therapy and refer patient for specialized care for assessment and treatment. If SJS or TEN is diagnosed, permanently discontinue I-O therapy.

27-Jun-2018

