## 4.5.2 Dose Delay Criteria

### 4.5.2.1 Dose Delay Criteria for Nivolumab and/or Ipilimumab (Arms A and B)

Nivolumab and/or ipilimumab administration should be delayed for the following:

- Any Grade  $\geq 2$  non-skin, drug-related AE, with the following exception:
  - Grade 2 drug-related fatigue does not require a treatment delay.
- Grade 2 drug-related creatinine,
- Any Grade  $\geq 3$  skin, drug-related AE
- Any Grade 3 drug-related laboratory abnormality, with the following exceptions for lymphopenia, AST, ALT, or total bilirubin and asymptomatic amylase or lipase abnormalities:
  - Grade 3 lymphopenia does not require dose delay
  - If a subject has a baseline AST, ALT, or total bilirubin that is within normal limits, delay dosing for drug-related Grade  $\geq 2$  toxicity
  - If a subject has baseline AST, ALT, or total bilirubin within the grade 1 toxicity range, delay dosing for drug-related Grade  $\geq 3$  toxicity
  - Any Grade  $\geq 3$  drug-related amylase or lipase abnormality that is not associated with symptoms or clinical manifestations of pancreatitis does not require dose delay.
- Any AE, laboratory abnormality, or intercurrent illness which, in the judgment of the investigator, warrants delaying the dose of study medication.

Subjects who have drug-related toxicities that meet the criteria for dose delay should have both drugs (ipilimumab and nivolumab) delayed until retreatment criteria are met (exceptions apply to the retreatment criteria after dose delay of ipilimumab and nivolumab for Grade  $\geq 3$  amylase and lipase abnormalities that are not associated with symptoms or clinical manifestations of pancreatitis and that are attributed to ipilimumab alone).

Subjects who require delay of nivolumab and ipilimumab should be re-evaluated weekly or more frequently if clinically indicated and resume nivolumab and/or ipilimumab dosing when re-treatment criteria are met.

Tumor assessments should continue as per protocol even if dosing is delayed. Periodic study visits to assess safety and laboratory studies should also continue every 6 weeks or more frequently if clinically indicated during such dosing delays.

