#### 4.5.4 Criteria to Resume Dosing

##### 4.5.4.1 Criteria to Resume Nivolumab or Ipilimumab (Arms A and B)

Subjects may resume treatment with study drug when the drug-related AE(s) resolve to Grade  $\leq 1$  or baseline value, with the following exceptions:

- Subjects may resume treatment in the presence of Grade 2 fatigue
- Subjects who have not experienced a Grade 3 drug-related skin AE may resume treatment in the presence of Grade 2 skin toxicity
- For subjects with Grade 2 AST, ALT, or total bilirubin elevations, dosing may resume when laboratory values return to baseline and management with corticosteroids, if needed, is complete.
- Subjects with combined Grade 2 AST/ALT AND total bilirubin values meeting discontinuation parameters (Section 4.5.5) should have treatment permanently discontinued.
- Drug-related pulmonary toxicity, diarrhea or colitis must have resolved to baseline before treatment is resumed. Subjects with persistent Grade 1 pneumonitis after completion of a steroid taper over at least 1 month may be eligible for retreatment if discussed with and approved by BMS Medical Monitor.
- Subjects with Grade < 4 drug-related endocrinopathies adequately controlled with only physiologic hormone replacement may resume treatment after consultation with the BMS Medical Monitor.

If dose delay is necessary, both nivolumab and ipilimumab must be delayed until treatment can resume. However, if a nivolumab-related infusion reaction prevents subsequent infusion of ipilimumab on the same day, the dose of ipilimumab should be replaced as soon as possible. In such instances, at least 37 days must elapse between the replacement dose of ipilimumab and the administration of the next dose of nivolumab combined with ipilimumab.

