#### **4.5.4.3 Criteria to Resume Nivolumab Combined with Fluorouracil and Cisplatin (Arm B)**

Subjects in Arm B may resume dosing only when criteria for BOTH resumption of nivolumab ([Section 4.5.4.1](#)) AND chemotherapy ([Section 4.5.4.2](#)) are met. That is, nivolumab and chemotherapy must be administered together until treatment discontinuation criteria ([Section 4.5.5](#)).

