### **4.5.5 Treatment Discontinuation Criteria**

#### **4.5.5.1 Nivolumab and/or Ipilimumab Treatment Discontinuation (Arms A and B)**

Treatment should be permanently discontinued for the following:

- Any Grade 2 drug-related uveitis, eye pain or blurred vision that does not respond to topical therapy and does not improve to Grade 1 severity within the re-treatment period OR requires systemic treatment
- Any Grade  $\geq 2$  pneumonitis with or without a causal relationship to nivolumab and/or ipilimumab
- Any Grade 3 non-skin, drug-related adverse event lasting  $> 7$  days or recurs, with the following exceptions for laboratory abnormalities, diarrhea, colitis, neurologic toxicity, drug-related uveitis, pneumonitis, bronchospasm, hypersensitivity reactions, infusion reactions, and endocrinopathies:
  - Grade 3 drug-related diarrhea, colitis, neurologic toxicity, myocarditis, uveitis, bronchospasm, hypersensitivity reaction, or infusion reaction of any duration requires discontinuation
  - Grade 3 drug-related endocrinopathies adequately controlled with only physiologic hormone replacement do not require discontinuation
  - Grade 3 drug-related laboratory abnormalities do not require treatment discontinuation except:
    - ◆ Grade 3 drug-related thrombocytopenia  $> 7$  days or associated with bleeding requires discontinuation
    - ◆ Any drug-related liver function test (LFT) abnormality that meets the following criteria require discontinuation:
      - Grade  $\geq 3$  drug-related AST, ALT or Total Bilirubin requires discontinuation
      - Concurrent AST or ALT  $> 3 \times$  ULN and total bilirubin  $> 2 \times$  ULN
- Any Grade 4 drug-related AE or laboratory abnormality (including but not limited to creatinine, AST, ALT, or total bilirubin), except for the following events which do not require discontinuation:
  - Grade 4 neutropenia  $\leq 7$  days
  - Grade 4 lymphopenia or leukopenia
  - Isolated Grade 4 amylase or lipase abnormalities that are not associated with symptoms or clinical manifestations of pancreatitis.

- Isolated Grade 4 electrolyte imbalances/abnormalities that are not associated with clinical sequelae and are corrected with supplementation/appropriate management within 72 hours of their onset
- Any drug-related Grade 4 endocrinopathy and Grade 3 adrenal insufficiency requires discontinuation

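### If a drug-related SJS/TEN event is graded 3, Appendix 1 stops immunotherapy permanently on diagnosis, but Section 4.5.5.1 has no unconditional stop for it and Section 4.5.4.1 permits restart

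*Protocol*

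**What the plan says.** **Appendix 1, Skin Adverse Event Management Algorithm.** On suspicion: "If SJS/TEN is suspected, withhold I-O therapy and refer patient for specialized care for assessment and treatment". On diagnosis: "If SJS or TEN is diagnosed, permanently discontinue I-O therapy". The footnote states no grade condition. The figure it belongs to is not shown in the text available.

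**Section 4.5.2.1 (dose delay, Arms A and B).** One reason to delay is "Any Grade $\geq 3$ skin, drug-related AE". On the length of the delay: "Subjects who have drug-related toxicities that meet the criteria for dose delay should have both drugs (ipilimumab and nivolumab) delayed until retreatment criteria are met".

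**Section 4.5.4.1 (resuming).** The general rule begins "Subjects may resume treatment with study drug when the drug-related AE(s) resolve to Grade" and sets the threshold at Grade 1 or lower, or baseline. A skin exception follows: "Subjects who have not experienced a Grade 3 drug-related skin AE may resume treatment in the presence of Grade 2 skin toxicity". For Arm B, Section 4.5.4.3 adds a second condition: "Subjects in Arm B may resume dosing only when criteria for BOTH resumption of nivolumab" and the chemotherapy resume criteria of Section 4.5.4.2 are met.

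**Section 4.5.5.1 (permanent discontinuation).** The Grade 3 rule opens "Any Grade 3 non-skin, drug-related adverse event lasting" more than 7 days, or recurring, and then lists exceptions. A separate rule stops treatment for Grade 4 drug-related events, with exceptions that concern laboratory findings only. SJS and TEN are not named.

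**Status of the two texts.** Section 3.5 makes discontinuation compulsory when a criterion in Section 4.5.5 is met; it does not cite Appendix 1. Section 4.5.7 refers investigators to the algorithms as an aid, and Appendix 1 introduces itself as guidance.

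**The concern.** A reader who takes one event, drug-related SJS (Stevens-Johnson syndrome) or TEN (toxic epidermal necrolysis) graded 3, through both parts of the protocol gets two different outcomes. The appendix ends treatment once the diagnosis is made. The numbered criteria treat the event as a Grade 3 skin toxicity, which means delay and possible restart.

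The compulsory list is the one that omits the stop; the text that contains it is presented as guidance. I found no rule saying which prevails. An investigator working from Section 4.5 could therefore restart nivolumab, with or without ipilimumab, without breaching any numbered criterion. What is at stake is patient safety in Arms A and B. No estimate, error rate, power figure or analysis depends on it.

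**Working it through.** The plan gives no figure to reproduce, so the check is a trace of the rules for a drug-related SJS/TEN event.

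| Step | Appendix 1, skin algorithm | Numbered sections |
|---|---|---|
| Suspected, Grade 3 | Withhold and refer | Delay (4.5.2.1), as for any Grade 3 or higher drug-related skin event |
| Diagnosed, Grade 3 | Permanent stop | No unconditional stop (4.5.5.1) |
| Resolved to Grade 1 or lower, or baseline | No restart | Restart permitted (4.5.4.1; Arm B also 4.5.4.2 and 4.5.4.3) |
| Diagnosed, Grade 4 | Permanent stop | Permanent stop (4.5.5.1) |

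*Does the skin exception in Section 4.5.4.1 bar restart?* No. It lets subjects without a previous Grade 3 skin event resume while still at Grade 2. A subject who has had one loses that option and falls back on the general threshold of Grade 1 or lower, or baseline.

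*Do the Arm B criteria bar restart?* No. Section 4.5.4.2 contains the same skin exception and does not mention SJS or TEN.

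*Which criteria in Section 4.5.5.1 can stop a Grade 3 drug-related skin event?*

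- Unconditional: 0, because the Grade 3 rule is limited to non-skin events.
- Conditional: 3.
  1. The event is classified as a Grade 3 hypersensitivity reaction, which stops treatment whatever its duration.
  2. The interruption exceeds 8 weeks for nivolumab or 12 weeks for ipilimumab. Prolonged steroid tapers for drug-related events are excepted, and the medical monitor must be consulted before restart after more than 8 weeks.
  3. The investigator judges that continued nivolumab poses a substantial clinical risk.

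Outside Section 4.5.5.1 there are further conditional routes. Section 3.5 compels discontinuation once the investigator judges that continuing is not in the subject's interest. In Arm B, Section 4.5.5.2 stops all drugs if the event cannot be attributed to nivolumab or to chemotherapy.

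*How much room does the interruption rule leave?* Nivolumab: 8 weeks / 2 weeks per dose = 4 dosing intervals. Ipilimumab: 12 weeks / 6 weeks per dose = 2 dosing intervals. A subject whose event resolves and who is redosed with nivolumab within 8 weeks of the previous dose does not reach the nivolumab limit.

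At Grade 3, then, the appendix attaches the stop to the diagnosis, while the body attaches it to classification, elapsed time, attribution or judgment.

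**The case against.** The best case against this is that the two texts can both be obeyed. Section 4.5.4.1 permits restart but does not require it, so an investigator who stops on diagnosis complies with everything. Section 4.5.7 sits in the dosing chapter, names skin among the algorithm topics and points to Appendix 1, where the instruction is explicit. Anyone who has diagnosed SJS or TEN also has an obvious basis for the judgment clauses in Sections 3.5 and 4.5.5.1. On this view a cross-reference is missing and nothing more.

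Much of this stands. A reader might infer that the numbered sections do nothing except delay and restart; the conditional stops listed above show that they do more. A reader might also infer that the protocol directs re-exposure; it does not. But compatibility by choosing the stricter text does not remove the gap. The stop that the sponsor evidently intends is absent from the list that Section 3.5 makes compulsory, and a restart would satisfy that list.

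A second objection is that the point rests on sources that cannot be seen. Appendix 1 refers grading to CTCAE v4, which is not reproduced; the algorithm's figure is missing; and the Investigator Brochure, which also carries the algorithms, is not available. This is fair. It means that whether, and how often, SJS/TEN would be graded 3 cannot be settled here. It does not alter the footnote, whose wording is complete without the figure.

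**Conclusion.** The point holds conditionally. If a drug-related SJS/TEN event is graded 3, the mandatory criteria permit a re-exposure that the sponsor's skin algorithm rules out, unless one of the conditional stops applies. This rests on three things: the Grade 3 assumption, the reading of the legible footnote as having no grade limit, and the absence of a rule of precedence.

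The documents do not support more than that. Both texts stop treatment at Grade 4. Nothing is claimed for events below Grade 3. The documents give neither an SJS/TEN incidence nor a grade distribution, so no number of affected subjects can be stated, and a reader should not infer that re-exposure is likely. The size of the point is therefore a count of rules: no unconditional and three conditional stops in Section 4.5.5.1. It should be corrected because the possible harm is to patients and the correction is small. It does not threaten the trial's conclusions.

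**What to change.** Add one criterion to Section 4.5.5.1: *Diagnosed SJS or TEN, regardless of grade: permanently discontinue nivolumab and ipilimumab (see Appendix 1, skin algorithm).* The words *regardless of grade* carry over the Appendix 1 rule and introduce no new clinical policy. Section 4.5.5.1 already names event-specific stops, and Appendix 6 records that Revised Protocol 04 added myocarditis there in the same way.

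A cross-reference in Section 4.5.2.1 to withhold on suspicion is optional, since that section already delays dosing for drug-related skin events of Grade 3 or higher. An exclusion in Section 4.5.4.1 is optional too, because a permanent stop already prevents restart.

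The cost is one line in a protocol amendment, with the IRB/IEC review described in Section 9.1.1. Data collection, sample size and analysis are unaffected.
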